1 - Grimace	Tight facial muscles; furrowed brow, chin, jaw (negative facial expression – nose, mouth brow)	
Cry		
0 - No cry	Quiet, not crying	
1 - Whimper	Mild moaning, intermittent	
2 - Vigorous cry	Loud scream; rising, shrill, continuous (Note: Silent cry may be scored if baby is intubated as evidenced by obvious mouth and facial movement)	
Breathing Pattern		
0 - Relaxed	Usual pattern for this infant	
1- Change in breathing	Indrawing, irregular, faster than usual; gagging, breath holding	
Arms		
0 - Relaxed/Restrained	No Muscular rigidity; occasional random movements of arms	
1 - Flexed/Extended	Tense, straight arms; rigid and/or rapid extension, flexion	
Legs		
0 - Relaxed/Restrained	No Muscular rigidity; occasional random movements of legs	
1 - Flexed/Extended	Tense, straight legs; rigid and/or rapid extension, flexion	
State of Arousal		
0 - Sleeping/Awake	Quiet, peaceful, sleeping or alert, random leg movements	
1 - Fussy	Alert, restless and thrashing	

Specify time antibiotics giving (before/after clean catch or before/after catheterization?)

.....

For the Doctor/nurse: Do you agree collecting urine using CCU(bladder massage) is easier than bladder catheterization? (Yes or No)

Parent satisfaction: are you satisfied with the used technique (Yes or No)

Physician name:

Signature:

Written informed consent:

Informed consent form

Research title

Clean Catch Urine Feasibility and Contamination Rate compared to Bladder Catheterization Urine in Pre-Continent Children: Randomized Control Trial

Research Idea

Our study aims to test an alternative way to urine collection by catheterization. primary outcomes are to compare the contamination rates between the two method and parent satisfaction. The secondary outcomes, include procedure duration, pain score (using neonatal infant pain scale)

Methodology

The patient will be randomly distributed into two groups: group one, urine will be collected through catheterization, group two urine will be collected by Clean Catch urine collection.

Contact information

If you have any questions, you may ask now or later, even after the study has started. If you wish to ask questions later, you may contact any of the following:

-Dr.[name] , contact number [name], E-Mail: [contact].
- [name]. [name], contact number [name], E-Mail: [contact]

- I am the parent of
- I have read the foregoing information, or it has been read to me. I have had the opportunity to ask questions about it.
- Any questions that I asked, they have been answered to my satisfaction. I consent voluntarily to participate as a participant in this research.

Authorized to consent name:

Relationship to the patient:

Signature date:

Researcher/Doctor:

Clean catch urine technique

Clean catch urine (bladder massage technique)

- Two people (trained nurses and/or physicians) were needed to perform the procedure, and a third to measure the time taken. This technique involves a combination of fluid intake and non-invasive bladder stimulation maneuvers .
- To provide breast-feeding or formula intake appropriate to the age and weight of the newborn. In babies fed infant formula, 10 ml was provided on the first day of life, increasing to 10ml per day during the first week. From the second week onwards, 25 ml/kg were administered before the onset of stimulation .
- Twenty-five minutes after feeding, the infant's genitals were cleaned thoroughly with warm water and soap and dried with sterile gauze .
- A sterile collector was placed near the baby to avoid losing urine samples.
- Hold the baby under their armpits with their legs dangling. One examiner then starts bladder stimulation which consists of a gentle tapping in the suprapubic area at a frequency of 100 taps or blows per minute for 30 seconds .
- Stimulation of the lumbar paravertebral zone in the lower back with a light circular massage for 30 s. Both stimulation maneuvers are repeated until micturition starts, and a midstream urine sample can be caught in a sterile collector.
- Success is defined as the collection of a sample within 5 min of starting the stimulation maneuvers.

Definitions for UTI, contamination, and insignificant growth

Urine culture results			
Definition	Urinalysis result	Organism(s) Cultured	Colony Threshold ^a
No growth	Negative	No growth	No growth
UTI	Positive ^b	1 Uropathogen ^c	≥100,000 CFU/mL
	Positive	1 Uropathogen	10,000–100,000 CFU/mL ^d
Contaminated	Negative	1 Non-uropathogen	≥100,000 CFU/mL
	Negative	≥2 Organisms (≥1 non-uropathogen)	Any colony count
	Negative	Mixed bacterial flora ^e	≥100,000 CFU/mL
Insignificant Growth	Positive or negative	1 Non-uropathogen	≤10,000 CFU/mL
	Negative	1 Non-uropathogen	≤100,000 CFU/mL

^aUrine culture colony counts had the same thresholds regardless of the method used to obtain the urine specimen (ie, urethral catheterization or bladder massage).

^bUrinalysis indicative for UTI-labeled positive: positive leukocyte esterase test and/or nitrite test, in addition to evidence of pyuria with >10 white blood cells per microliter. Urinalysis results that do not meet criteria for positive are considered negative.

^cThe identified organism is considered a uropathogen based on clinical judgment of the provider caring for the patient.

^dFor this range, providers must consider the patient's clinical presentation and whether the urinalysis supports the diagnosis of a UTI.

^eNomenclature indicating growth of 3 or more organisms.

Study flow chart

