Job Title:	MD, FRCPc, Fellow in ICU and Sports Medicine. Emergency medicine consultant.
Email:	[contact]
Phone	[name]
Co-investigator:	
Title and Name:	[name] [name]
Staff ID:	80828
Job Title:	Pediatric specialist, OMSB
Email:	[contact]
Phone	[name]

2. Summary:

Introduction: Urinary tract infections (UTIs) are a common source of infection in children, accounting for a significant proportion of visits every year. Diagnosing UTIs requires obtaining a urine specimen, which can be collected using four methods: invasive techniques, such as suprapubic aspiration and urethral bladder catheterization, and noninvasive techniques, such as sterile bag and clean catch. However, catheterization can be a painful and invasive procedure, particularly in young infants who are less cooperative, and sometimes tends to be rejected by parents.

Given the availability of alternative methods with comparable contamination rates, we aim to investigate the feasibility and contamination rate of clean catch urine compared to bladder catheterization, as well as secondary outcomes such as pain scores, parental satisfaction, and time required to collect urine for each technique.

Methods: To achieve this, we will conduct a randomized control trial in precontinent pediatric patients. A pilot study with 40 samples in each arm will be conducted since there is no prior information about contamination rates in our setting. A well-designed and labeled data collection sheets will be used for data collection, and the data will be entered using EPI-data software. Statistical analysis will be performed using IBM SPSS statistics.

Aim: The main aim of this study is to introduce clean catch urine (bladder massage technique) to our setting, and to compare its feasibility with the bladder catheterization which is the standard practice.

Patient Population: young infants from 0 to 6 months of age

Intervention: There will be two groups:

1. Group A (Experimental group): Urine samples will be collected using the clean catch urine method (bladder massage technique).
2. Group B (Control group): Urine samples will be collected using the standard bladder catheterization method.

Clinical Measurement: All collected urine samples will be labeled and sent to the laboratory. All results will be retrieved from the medical records. Direct measurement will be for the duration of the procedures in both experiment and

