control group (stopwatch will be used). Pain score (Neonatal Infant Pain Scale) and parental satisfaction survey will be filled at the time of the procedure.

Outcome: Contamination rate and feasibility of both urine sampling techniques

3. Introduction: literature review and justification of the study.

Urinary tract infection (UTI) is a common source of infection in children. It accounts for 5 to 14 percent of visits by children every year [1]. The overall prevalence is around 7% among different age subgroups of children. Several factors affect the prevalence of UTI including age, gender, and circumcision status [2].

The diagnosis of UTI requires obtaining a urine specimen from the patient. Generally, there are four methods used in collecting urine samples which can be categorized as invasive (such as suprapubic aspiration and urethral bladder catheterization) and noninvasive (such as Sterile bag and clean catch) [3].

The selection of the urine collection technique is mainly determined by whether the patient is toilet-trained or not. In non-toilet-trained patients, urethral bladder catheterization or suprapubic aspiration can be used. The latter is having the least contamination rate in urine culture [3]. Clean-catch urine is commonly used for toilet-trained patients. If the clinical assessment of febrile infants necessitates immediate antimicrobial therapy, urine culture should be obtained either by urethral bladder catheterization or suprapubic aspiration [3, 4].

Previous observational studies showed approximately a 1 percent contamination rate using the suprapubic aspiration technique [5,6,7,8,9]. In a prospective study done on premature infants it was found that the suprapubic aspiration technique resulted in increased pain and a higher probability of procedural failure compared to urethral bladder catheterization [10]. According to American academy of pediatrics (AAP), for non-toilet trained children, it's advisable to gather a urine sample through methods like ureteral catheterization or suprapubic bladder aspiration, especially when a sample obtained using a perineal bag shows positive results on a dipstick test [11]. The latest guideline from AAP recommends urine culture to be obtained via either SPA or bladder catheterization in pediatric patients aged between 8 to 60 days old, due to false positive results that can occur in the other urine collection techniques [12].

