To compare procedure duration in both methods. And pain score (using neonatal infant pain scale)

Study hypothesis

- The contamination rate of clean catch urine sampling is similar to the bladder catheterization.
- Less painful as it is less invasive.

5. Feasibility of the study

It is a multicentered study which enrolls pediatric patients who need urine collection according to the mentioned inclusion criteria. Notably, urinary tract infection (UTI) is a very common presentation in this age group, and it should be considered in almost all pediatric patients with fever with no clear source of infection. All the previously mentioned points can assure that the targeted sample size can be achieved within the designated timeline.

6. Research Design and Methods

Study design:

This pilot study will be conducted as randomized controlled trial.

Characteristics of study area and target population:

Study will be conducted in a tertiary hospital, pediatric emergency, and pediatric ward. Target population are pediatric patients aged between 0 to 6 months.

Primary and secondary endpoints:

Primary endpoints: Urine culture contamination rate and parental satisfaction

Secondary endpoints: Pain score (utilizing Neonatal Infant Pain Scale) and duration of the procedures.

Selection and withdrawal of subjects:

All infants younger than 6 months of age, who require urine sample as part fever work-up in emergency department.

Any subject may be withdrawn from the study at any time for any reason and without penalty or prejudice.

Sampling and sample size:

A pilot study with 40 samples in each arm will be conducted since there is no prior information about contamination rates in our local setting.

7. Randomization

The study will utilize computerized block randomization technique to assign participants into experimental and control groups, with each block being randomized to ensure unbiased allocation. The randomization will occur in the emergency triage.

8. Study flow

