Patient will be assessed in triage and cases to be included in the study as per the inclusion criteria, after that patients will be randomized using computerized block randomization technique into two groups. Then, patients will be assigned to a bed, pulse oximetry to be applied, data collection sheet to be filled, confirm that infant had good feeding/ didn't pass urine over last 20 minutes and proper cleaning to be done. The next step will be, collecting urine sample according to randomization group. Group A patients (control group), urine to be collected by standardized catheterization technique while group B by standard CCU technique. Meanwhile, time of each procedure to be documented. Regarding group B , after collecting urine by CCU , we recommend to collect another sample by catheterization to guide the management and antibiotic choice. (Appendix: Study flow chart)

9. Study procedures

Clean catch urine (bladder massage technique) provided in the appendix.

10. Variable definitions and measurements

Data collection tools and methods: (provided in the appendix)

Data quality:

In each site there will be a focal point doctor, responsible for the site. Before conducting the study, we will do training sessions about the study and we will prepare a video teaching the physicians/ nurses the steps of urine collection of by clean catch technique. Individual meetings to be conducted with the focal point for each site to clarify their inquiry. We will use a research assistant for data collection to facilitate the process and to help monitoring the flow of the study protocol.

Data analysis: We will use Statistical Package for the Social Sciences (SPSS) applications version 25 for our analysis.

11. Ethical considerations

Already we have the ethical approval from the ministry of health of Oman (proposal ID: MoH/CSR/23/26368), all recommended changes were adjusted before starting the study. If any risk on patient safety noticed during our study, we will make sure to stop the study protocol. We are not anticipating any harm to patient as the technique our study introducing is less invasive and more comfortable to patients. For the patient group with CCU collection, we are recommending another sample of urine to be collected to guide the antibiotics choice as CCU contamination rate and accuracy will be studied by this paper.

12. Conflict of interest

No conflict of interest

13. Incentives

No incentives of any kind will be given to the participants.

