14. Results Dissemination

The study results will be disseminated through various channels to ensure wider reach and maximum impact. This includes local and international publication of the

study in peer-reviewed journals, as well as presentation of findings at relevant conferences and symposiums. Additionally, we plan to share the study outcomes with relevant stakeholders such as healthcare professionals, policymakers to ensure that the findings are effectively translated into practice and policy.

15. Management and monitoring of the research activities

Each focal point will be responsible for that hospital work flow. As each focal point will be in direct contact with the workers at the specific site. Daily monitor to be done to check the new enrolled cases. The other researchers to follow the whole workflow weakly by contact the assigned focal point.

16. Limitations and difficulties of the study:

1. Constrained timeframe for research due to residency program obligations
2. Ensuring an adequate sample size

17. Rationale for subject selection and recruitment.

This is a randomized control study, aiming to study the feasibility and contamination rate of urine collected by clean catch technique comparing to catheterization technique. The population enrolled in this study, pediatric patients, that will benefit of introducing clean catch technique. This is a population who cannot give urine sample for laboratory testing without catheterization which is a painful procedure. The clean catch technique will be of much help for this age group as it is painless and less invasive technique. Therefore, it seems highly beneficial to study the contamination rate of CCU collection in order to introduce it in local guidelines to replace the current use of catheterization.

18. Statistical analysis:

For data entry purposes Microsoft Excel software will be used and for the data analysis IBM SPSS statistics will be used. Normally distributed continuous data will be analyzed using student T test, if abnormal MANN-WHITNEY test will be used. For categorical comparisons CHI-square test will be applied. P-value of less than 0.05% will be considered as statistical significance.

19. Criteria for terminating the study.

A subject who is included in the study, and failed urine collection by CCU , will be removed from study and counted as CCU collection failure. After that to be managed by in-charged doctor as per the treating doctor plan.

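### The only staff question on ease asks for agreement that clean catch is easier, whichever technique was used, so it gives no randomized comparison of ease

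*Protocol*

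**What the plan says.** Protocol section 2 (Summary) and the end of section 3 (Introduction) give the main aim as introducing clean catch and "to compare its feasibility with the bladder catheterization which is the standard practice". The Summary names the outcome as "Contamination rate and feasibility of both urine sampling techniques".

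The endpoint list in section 6 is narrower. It reads "Primary endpoints: Urine culture contamination rate and parental satisfaction", with pain score and procedure duration as secondary. Staff ease is not listed.

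The data collection sheet (section 24, Appendix) is one form with a tick box for the technique. It asks the doctor or nurse "Do you agree collecting urine using CCU(bladder massage) is easier than bladder catheterization? (Yes or No". The next line asks the parent "Parent satisfaction: are you satisfied with the used technique (Yes or No". No other staff rating of ease appears.

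Section 8 (Study flow) assigns one technique per infant: "The next step will be, collecting urine sample according to randomization group". For the clean-catch arm it adds: "after collecting urine by CCU , we recommend to collect another sample by catheterization to guide the management and antibiotic choice".

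**The concern.** A randomized comparison of ease needs each collection to be rated on the same scale, so that ratings of clean catch in one arm can be set against ratings of catheterization in the other. The parent item has that form: it asks about the technique the infant received. The staff item does not. It asks everyone for the same general opinion, states one answer in the question, and allows only Yes or No.

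At stake is one part of the feasibility comparison. If the item stays, the trial will hold up to 80 answers on ease from which the ease of either technique cannot be recovered. An analysis plan cannot repair this, because the rating would never have been collected.

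**Working it through.** The protocol gives no figure for staff ease, and its 40 per arm comes without a calculation, so there is nothing to reproduce. The check is of what the item can measure. All percentages and staff numbers below are assumptions for illustration; only the 40 per arm (80 sheets) is from the protocol.

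**1. Between-arm comparison.** Let *q* be the share of staff who hold that clean catch is easier. If the same pool of staff answers in both arms and their opinion is settled, the expected Yes rate is *q* in each arm.
- *q* = 50%: 20 of 40 against 20 of 40; expected difference 0; 95% half-width 1.96 × √(2 × 0.5 × 0.5 / 40) = 21.9 points.
- *q* = 70%: 28 of 40 against 28 of 40; expected difference 0; half-width 1.96 × √(2 × 0.7 × 0.3 / 40) = 20.1 points.

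The chi-square test that section 18 names for categorical comparisons would then target zero whether clean catch is much easier or no easier. A difference would arise only if the procedure just done changed the respondent's opinion, or if different people answered in the two arms. Neither is a difference in ease.

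**2. What the respondent has seen.** In the catheter arm the design includes no clean catch on that infant. In the clean-catch arm a catheter sample is recommended afterwards, so the respondent may have done both. The sheet does not say when the item is answered or whether one person did both procedures. The basis for the answer therefore differs by arm and is not recorded.

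**3. Direction of the wording.** Let *e* be the share who find clean catch easier and *s* the share who see no difference. Read literally, those in *s* should answer No, so the Yes share is *e*. If the leading wording carries all of them to Yes, it is *e* + *s*.
- With *e* = 40%, *s* = 40% and 20% finding it harder, 80 sheets give 32 Yes (40%) at one end and 32 + 32 = 64 Yes (80%) at the other.
- The gap equals *s*: 20, 40 or 60 points if *s* is 20%, 40% or 60%.

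One set of opinions can thus look like a minority or a large majority for clean catch. The documents do not say where in the range the answers would fall.

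**4. Repeat respondents.** With *m* answers per person and within-person correlation ρ, the effective number is 80 / (1 + (*m* − 1)ρ), and an interval that treats all 80 as independent is too narrow by √(1 + (*m* − 1)ρ).
- 10 people, 8 answers each: ρ = 0.5 gives 80/4.5 = 17.8 (factor 2.1); ρ = 0.9 gives 80/7.3 = 11.0 (factor 2.7).
- 40 people, 2 answers each: ρ = 0.5 gives 80/1.5 = 53.3 (factor 1.2); ρ = 0.9 gives 80/1.9 = 42.1 (factor 1.4).

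Neither the number of staff nor ρ is in the protocol, so no single figure can be defended.

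**5. What else informs feasibility.** Duration is recorded in both arms. Failed clean catches are counted (section 19), and success within five minutes is defined in the Appendix for clean catch only. The sheet has no success or failure field. Duration is thus the one other direct feasibility measure taken the same way in both arms.

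**The case against.** The strongest reply is that this is a wording comment on an unlisted item in a pilot. Staff ease is in neither endpoint list, no analysis of it is described beyond the general chi-square sentence, and duration and failure counts are more objective. The item also yields a crude staff opinion, which has some use. All of this stands, and it limits the importance of the point. It does not make the item a measure of ease by arm.

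Four stronger readings are tempting, and the documents do not support them:
- *Every respondent judges after a single procedure.* By design this holds only in the catheter arm, because of the second sample recommended in section 8. Nor can it be said that catheter-arm staff have never done a clean catch; section 6 does not exclude it, and section 10 plans training sessions and a video.
- *The item will favour clean catch.* Leading wording and the missing tie option push in opposite directions. Section 17's remark that "it is painless and less invasive technique" concerns the infant's experience and is no evidence about staff answers.
- *The 80 answers are worth only a dozen or so.* That needs a small staff and a high correlation, neither of which is documented.
- *Feasibility rests on this question alone, and the tally will be reported as proof of it.* Other measures exist, and the protocol does not say how the item will be reported.

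**Conclusion.** The point holds in a limited form. The only staff item on ease is leading, identical in both arms and silent on the technique used, so it provides no randomized comparison of ease. That follows from the text and needs no assumption about staff numbers. A net bias from the wording is likely but not shown. Answers from the same person would not be independent, to a degree that cannot be computed from the protocol.

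The importance is modest, because ease is not a listed endpoint. The point is still worth acting on: feasibility against catheterization is the main aim and a named outcome, the other measures cover it only in part, and the correction is cheap.

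**What to change.** Replace the item with a neutral ordered rating of the collection just performed, for example 1 (very difficult) to 5 (very easy), worded identically in both arms and compared between arms. State that it refers to the randomized collection and, in the clean-catch arm, is completed before any second sample. Complete it for failed collections too, since the hardest cases would otherwise drop out.

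Add an identifier for the respondent or operator, so that repeat respondents can be accounted for in the analysis. The sheet now records only the physician's name. The item is addressed to a doctor or nurse, and the Appendix has clean catch done by two people who may be either, so that name need not be the respondent's.

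If a head-to-head preference is wanted, ask each operator once at study end, with the options clean catch, catheter or no difference.

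The cost is about two changed lines on the sheet, with no added visits or procedures. The downside is that the per-infant tally of which is easier is lost or moved to study end. Ratings will still come from staff who know the technique; neutral wording does not remove that.

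### The consent form does not mention the further catheter sample that the protocol recommends in the clean-catch arm, and the primary satisfaction item does not say which of the two procedures it covers

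*Protocol*

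**What the plan says.** **Consent form (Appendix, Methodology).** Each group is given one method. For the control arm: "group one, urine will be collected through catheterization". For the experimental arm: "group two urine will be collected by Clean Catch urine collection". No further sample is mentioned for either group.

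**Section 8 (Study flow).** Once urine has been obtained by clean catch in that group: "we recommend to collect another sample by catheterization to guide the management and antibiotic choice". No dipstick result or subgroup is attached as a condition.

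**Section 11 (Ethical considerations).** For the same group: "we are recommending another sample of urine to be collected to guide the antibiotics choice". The method of this second sample is not named here.

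**Section 6.** "Primary endpoints: Urine culture contamination rate and parental satisfaction".

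**Data collection sheet (Appendix).** Satisfaction is a single item: "Parent satisfaction: are you satisfied with the used technique (Yes or No". The field for the collection method offers clean catch or catheterization.

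**Section 2 (Clinical Measurement).** On timing: "parental satisfaction survey will be filled at the time of the procedure".

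**The concern.** A parent who reads the consent paragraph would reasonably take group two to be the arm without a catheter. The study flow recommends a catheter sample in that arm once clean catch has worked. The protocol itself treats this as a matter of weight to families: Section 2 describes catheterization as painful, invasive and at times refused by parents, and Section 17 contrasts it with a painless clean catch. The procedure left out of the form is therefore the one that the trial is meant to spare infants.

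The second stake is measurement. Parental satisfaction is a primary endpoint. In the catheter arm there is one procedure to rate. In the clean-catch arm there may be two, and the single yes/no answer may describe the clean catch, the catheter or the whole episode. Because this can happen in one arm only, a comparison of the arms could mix the effect of the technique with the effect of what followed it.

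**Working it through.** The check is mainly a comparison of texts. The plan gives no figure of its own on this point to reproduce.

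**Step 1: is it the same arm?** The group letters differ. Section 2 calls clean catch Group A, and Section 8 calls it group B. Section 8 names the clean-catch technique in the sentence concerned, so the arm is clear, and it is group two in the consent form.

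**Step 2: what each text says about a second sample in that arm.**

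| Place | First sample | Second sample |
|---|---|---|
| Consent form, Methodology | Clean catch | Not mentioned |
| Section 8 | Clean catch | Recommended, by catheterization, no condition stated |
| Section 11 | Clean catch | Recommended, method not named |

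The consent form omits what Section 8 recommends. Section 11 agrees with Section 8 that there is a second sample but does not say how it is taken.

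**Step 3: how many infants.** The recommendation follows a clean-catch sample. Under Section 19, a failed clean catch takes the infant out of the study, counted as a failure, and into the treating doctor's plan. The number concerned is therefore

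allocated infants × clean-catch success rate.

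Inputs: 40 per arm (Section 6), and the success rates quoted in Section 3, which are 61% at the lowest, 86.3% in between and 90% at the highest.

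- Low: 40 × 0.61 = 24.4, about 24 infants
- Middle: 40 × 0.863 = 34.5, about 35 infants
- High: 40 × 0.90 = 36 infants

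This assumes that 40 means infants allocated. Section 6 speaks of 40 samples per arm. If only collected samples were counted towards the 40, each of the 40 would have had a successful clean catch. The documents do not settle which is meant, and 24 to 36 is the cautious reading.

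**Step 4: what the satisfaction item measures.**

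- *Referent.* It asks about the technique that was used. With one procedure this is clear. With two it is not.
- *Timing.* It is completed when the procedure is done. With two procedures this could be after the first or after the second.
- *Record.* The sheet has one field for the collection method. A free-text line asks whether antibiotics came before or after each procedure, but no field states that a second procedure was done. An analyst could not reliably tell which clean-catch answers followed a catheter.

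**The case against.** The strongest reply is that the form describes the randomized method and need not list every later step of care. The second sample is recommended, not required, and its purpose is treatment. Section 3 shows that catheterization is already part of local practice, for instance after a positive dipstick from a bag sample. Part of this stands: the second sample is not an assigned intervention. It does not remove the point. Section 8 attaches no dipstick condition and makes the recommendation for one randomized arm, so it goes beyond the bag-sample pathway in Section 3 and belongs in what parents are told.

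A second reply is that consent pages were removed from the file, and the flow chart is not shown, so a fuller information sheet may exist. That cannot be excluded. The Methodology sentence does read as complete, however, and as it stands it would still not match Section 8.

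Several stronger readings are tempting but unsupported:

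- **That the form promises clean catch only.** It does not use that word. The fault is an omission, not an explicit false statement.
- **That the satisfaction endpoint rests on the consent wording.** The item asks about the technique used, at the time of use. Its ambiguity comes from the study flow and the item itself. Surprise, refusal or a negative answer caused by the form is plausible, but it is inference.
- **That a particular shift in satisfaction can be expected.** Nothing in the documents indicates how many answers would change.
- **That the harm statement in Section 11 is false.** It reads "We are not anticipating any harm to patient as the technique our study introducing is less invasive and more comfortable to patients". That describes the technique, and the sentence after it discloses the further sample to the ethics reader. It does not describe all that the arm may receive, but it conceals nothing.

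**Conclusion.** The point holds as an omission and an ambiguity. The consent Methodology shown leaves out a catheter sample that Section 8 recommends after clean catch, so the consent text and the study flow must be reconciled. About 24 to 36 of 40 clean-catch infants would be concerned. This assumes 40 infants allocated, success within the range of the cited studies, and a recommendation applied as written. How many parents would accept the second sample is unknown.

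Separately, in that arm only, the primary satisfaction item does not fix which procedure is rated or when. Correcting the form alone would leave this untouched. The size and direction of any distortion cannot be derived from the documents.

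The conclusion rests on the consent text in the file being what parents receive. It is worth correcting before enrolment, but it does not by itself invalidate the design.

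**What to change.** 1. Reconcile the consent Methodology with Sections 8 and 11, and have Section 11 agree with Section 8 on how the second sample is obtained. Parents should be told before randomization whatever the protocol finally sets for that sample. Whether it should be taken is for the clinical investigators and is not judged here.
2. Word the satisfaction item so that it refers to the allocated technique, and have it answered before any second sample. Alternatively, record satisfaction separately for each procedure and name the allocated technique as the endpoint.
3. Add a field to the data collection sheet for whether a second procedure was done, so that the number of clean-catch infants who had one is known.

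The cost is a change of wording in the consent form and the protocol, a small change to the data sheet, and an ethics notification. No extra patients or procedures are needed.
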